6.3.2 Baseline data

The following demographic characteristics will be summarized by treatment group and overall:

- Age
- Sex
- Child bearing potential among Female
- Participating country
- Ethnicity (e.g White caucasian; White mixed; Asian, Black; Other)
- Population group (AIDS with any CD4 cell count; Severe bacterial infection and CD4 cell count < 200; Asymptomatic with CD4 cell count < 100; Currently receiving treatment for an opportunistic infection)
- Body weight and BMI
- Systolic and diastolic Blood Pressure
- Pulse rate
- Alcohol intake (Does not drink alcohol; Drink alcohol)
- Smokers (Never smoked; Current smoker; Ex-smoker)
- Recreational drug use
- Days from HIV diagnosis to treatment initiation
- HIV RNA viral load, log10 copies/mL and in category (<100,000; 100,000-500,000; >500,000)
- CD4+ count (cells/ μ L) and in category (<50; 50-199; \geq 200) and CD4+ (%)
- CD8+ count (cells/ μ L) and CD8+ (%)
- CD4/CD8 ratio and in category (<0.10; 0.10-0.30; >0.30)
- Positive HBV Antigen; Positive HCV antibody:
- HCV RNA Viral load among those with Positive HCV antibody
- Positive TB testing result
- Red blood cells ($10^{12}/L$);
- White blood cells ($10^{12}/L$)
- Platelet counts ($10^9/L$)
- Haemoglobin (g/dL)
- Haematocrit (%)
- MVC (fl)
- MCH (pg)
- Neutrophils ($10^{12}/L$)
- Lymphocytes ($10^{12}/L$)
- Monocytes ($10^{12}/L$)
- Eosinophils ($10^{12}/L$)
- Basophils ($10^{12}/L$)
- Sodium (mmol/L)
- Potassium (mmol/L)
- Total Protein (mmol/L)
- Total Bilirubin (μ mol/L)
- Indirect bilirubin (μ mol/L)
- ALT (U/L); AST (U/L)
- Albumin (g/L)
- Creatinine (umol/L); Creatinine clearance (eGFR) (mL/min)
- Alkaline phosphatase (U/L)
- Creatine phosphokinase (U/L)
- Calcium (mmol/L)
- Phosphate (mmol/L)
- Urea (mmol/L)

- Chloride (mmol/L)
- Total cholesterol (mmol/L); HDL-cholesterol (mmol/L); LDL-cholesterol (mmol/L); Triglyceride (mmol/L);
- Glucose (mmol/L)
- Resistance mutations at baseline. Drugs resistance mutations will be identified from the Stanford drugs resistance interpretation algorithm (last version at the time of analysis).
<https://hivdb.stanford.edu/dr-summary/mut-scores/NRTI/>;
<https://hivdb.stanford.edu/dr-summary/mut-scores/NNRTI/>; <https://hivdb.stanford.edu/dr-summary/mut-scores/PI/>; <https://hivdb.stanford.edu/dr-summary/mut-scores/INSTI/>.

6.4 STUDY TREATMENT COMPLIANCE

Adherence during the trial will be monitored by subject questioning regarding missed tablets at each visit. Compliance rate for each participant will be estimated by the response of the following item: Thinking about the last week, how often has the subject taken their medication? The response is classified in 5 categories (All the time, Most of the time, About half of the time, Very few times, None). For participants who reported taking their medication "All the time" during the past week, if it is also indicated that they forgot to take their medication at least once since the last visit, they are downgraded to the "Most of the time" category. The compliance rate will be done at each visit. A bar plot will be presented.

6.5 STRATIFICATION FACTOR

The stratification variable is consisted of two variables: participating country (7 countries: UK, Spain, France, Belgium, Germany, Ireland, and Italy) and baseline CD4 cell count (<50, 50-199, ≥200). Overall, 21 strata will be considered. Based on the large number of strata, we anticipated some few participants in some strata. In country that will recruit fewer than 10 participants, we will group together some neighboring countries. In addition, with regard to CD4 cell count, we will group together participants whose value is between 50-199 and ≥200/µl to obtain 2 categories (<50 versus ≥50/µl) because of the anticipated small number of participants in the latter category. These new variables will be used for adjustments.

The number and proportion of participants in each stratum will be reported by treatment group and overall. The exact list of strata will also be presented.

7. EFFICACY ANALYSES

All the efficacy analyses of the primary and secondary endpoints will be conducted on the mITT population and a sensitivity analysis of the per-protocol population.

Time-to-event methods, including Kaplan-Meier, Cox proportional hazard models, and Poisson regression models, will be used to account for all participants in the analysis.

7.1 PRIMARY EFFICACY ANALYSIS

Endpoint

The primary endpoint is the first occurrence of any of the following components:

1. Virological failure
 - a) Insufficient virological response, either:
 - a. HIV-1 RNA reduction < 1 log 10 copies/mL at week 12, or
 - b. Viral load > 50 HIV-1 RNA copies/mL at week 48
 - b) Viral rebound, which is subsequently confirmed at the following scheduled or unscheduled visit, defined as either:
 - a. Rebound of HIV-1 RNA to >200 copies/mL after having achieved HIV-1 RNA <50 copies/mL
 - b. Rebound of HIV RNA by >1 log 10 copies/mL from nadir value, for patients whose viral load has never been suppressed below 50 copies/mL
2. Clinical events¹
 - a) Death related to HIV, AIDS, OI/severe BI or complications of therapy including IRIS
 - b) Any new or recurrent AIDS defining event on, or after 28 days of therapy
 - c) Any new serious non-AIDS defining event documented by the endpoint review committee (including severe BI, end stage liver disease, renal failure, cardiovascular event, and non-AIDS related malignant disease)
 - d) Clinically relevant AEs of any grade or IRIS which require treatment interruption (lasting > 5 days) of INI or boosted PI therapy within the first 48 weeks after randomisation. Discontinuation of BIC or boosted DRV followed by (within 5 days) continuation with another INI or PI, respectively, is not considered as a strategy failure or endpoint.

Descriptive statistics and graphical representation

The analyses will be performed with the mITT population and DPS1. Data will be summarized with the number and percentage of participants with an event. Kaplan-Meier curves will also be plotted for the primary endpoint and its component.

A table, listing for each participant any event, they may have had as well as the day from baseline to event onset, will be generated.

Statistical methodology

The proportion of patients with an event will be estimated using the Kaplan-Meier method. Episodes of clinical events diagnosed at baseline will not be considered as incident events in the study. For virological events evaluation data were censored at the time of treatment discontinuation.

The follow-up will begin at baseline and continue until the week 48 visit, study discontinuation, loss to follow-up, or onset of the composite primary endpoint events; whichever occurs first. Participants lost to follow-up or who have discontinued the study when they are endpoint free at time of leaving the study will be censored at the date of last observation.

The effect of study treatment will be assessed using Cox regression model with treatment group and adjustments for stratification factor (country/group of neighbouring countries and baseline CD4 cell

counts ($<50/\mu\text{L}$ or $\geq50/\mu\text{L}$), as the sample size would not allow use of the stratification factors of randomisation (country and baseline CD4 in three categories (<50 ; $50-199$; $\geq200/\mu\text{L}$)). An adjusted hazard ratio (HR) and the associated 95% Confidence Interval (CI) will be calculated. Separate analyses for each component of the primary endpoint will be done. All P-values will be two-tailed with a significant level at 5%.

A sensitive analysis will be performed with the per-protocol population and DPS2.

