5.2.1 Full Analysis Population

Modified Intention-to-treat (mITT) analysis set: all randomised participants who received at least one dose of study drug. Participants will be included in the analyses according to the planned randomised intervention.

The following data points sets are defined:

- **DPS1:** All observed data will be included in the analysis set regardless of study intervention discontinuation and/or receipt of rescue therapy
- **DPS2:** For participants who discontinue study intervention and/or receive rescue therapy, post-discontinuation or post-rescue observations will be excluded.

The mITT and DPS1 will be used to estimate the primary endpoints and the all secondary endpoints.

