5.2.2 Per Protocol Population

The per-protocol (PP) population will include all participants from the mITT population, with the exception of those who did not meet the inclusion/exclusion criteria or who initially received treatment assigned to the other group.

The PP and DPS2 will be used for sensitivity analyses of the primary endpoint.

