7.2 SECONDARY EFFICACY ANALYSES

7.2.1 Cumulative incidence of the composite primary endpoint

Endpoint

Cumulative incidence of the composite primary endpoint. All the observed events for each patient over the total duration of follow-up will be considered. Patients with multiple events on a given day will be considered as having one event on that day. For virological events only first episode was considered and data were censored at the time of treatment discontinuation.

Descriptive statistics and graphical representation

The cumulative incidence of the primary composite endpoint will be summarized with the total number of events, person-years, and the incidence rates per 100 person-years by treatment group (Integrase inhibitor versus Protease inhibitor).

Statistical methodology

In this analysis, the event is the sum of all episodes of the composite primary endpoint. For this analysis, the entire follow-up will be considered (i.e. follow-up will begin at baseline and continue until the 48-week visit, study discontinuation, loss to follow-up; whichever occurs first). All participants will be censored on the date of their last observation.

The cumulative incidence of the composite primary endpoint will be estimated by the total number of events divided by the total number of person-years of observation. The person-year is the total sum of the number of years that each subject of the study population has been under observation. The number of years each subject would have been under observation will be calculated by the difference between the date of the last observation and the date of study treatment initiation plus one, divided by 365.25.

The effect of study treatment will be assessed using a Poisson regression model adjusted for the stratification factor (country/group of neighbouring countries and baseline CD4 cell counts (<50 or $\geq50/\mu\text{L}$)). An adjusted incidence rate ratio (IRR) and the associated 95% CI will be calculated.

All P-values will be two-tailed with a significant level at 5%.

This analysis will only be performed if it is added additional information: i.e. if the number of cumulative episodes is greater than that of the first episode (with at least 10 additional events).

7.2.2 HIV-RNA viral load <50 copies/mL at week 24, 36 and 48

Endpoint

The proportion of patients with HIV-RNA viral load <50 copies/mL at week 24, 36 and 48 using the snapshot approach.

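### The SAP puts the primary composite on all observed data (mITT/DPS1) but censors its virological events when treatment stops, leaving an undefined hybrid that protocol 9.3 does not contain

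*Combined protocol and SAP*

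**What the plan says.** SAP 5.2.1 defines DPS1 as follows: "All observed data will be included in the analysis set regardless of study intervention discontinuation and/or receipt of rescue therapy". It gives DPS1 its role: "The mITT and DPS1 will be used to estimate the primary endpoints and the all secondary endpoints". DPS2, defined in the same section, drops whatever is observed after discontinuation or rescue. SAP 5.2.2 limits its use: "The PP and DPS2 will be used for sensitivity analyses of the primary endpoint".

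SAP 7.1 repeats the assignment under descriptive statistics: "The analyses will be performed with the mITT population and DPS1". Its statistical methodology then adds: "For virological events evaluation data were censored at the time of treatment discontinuation". The next paragraph gives the end of follow-up: "continue until the week 48 visit, study discontinuation, loss to follow-up, or onset of the composite primary endpoint events; whichever occurs first". Stopping treatment is not in that list. The section ends: "A sensitive analysis will be performed with the per-protocol population and DPS2".

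SAP 7.2.1, the recurrent-event version of the composite, carries the same rule: "For virological events only first episode was considered and data were censored at the time of treatment discontinuation".

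Protocol v5.0 section 9.3 (same text in v1.5) keeps switchers in their randomised arm and censors endpoint-free patients who are lost or leave the study. It has no rule tied to stopping study drug. Protocol 6.5 lets the investigator stop study drug, giving lack of efficacy as an example, and continues follow-up to week 48, with attendance encouraged.

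**The concern.** The conflict lies inside the primary estimator. One analyst, following the data-set definition, the follow-up paragraph and the protocol, would use viral loads after a stop. Another, following the censoring sentence, would not. Both could cite section 7.1, and their hazard ratios could differ.

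Take a patient whose study drug is stopped for lack of efficacy at week 30 before any criterion is met. Protocol 9.3 read with DPS1 assesses the week-48 viral load. The 7.1 sentence does not. The snapshot in SAP 7.2.2 classes the same patient as HIV-RNA at or above 50 copies/mL. A stop between a first rebound value and its confirming visit could also lose the event. Because such stops reflect prognosis, the censoring can be informative.

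Two definitions are missing:

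- Treatment discontinuation could mean the allocated tablet, the drug class or all antiretroviral therapy. SAP 7.1 says a within-class change within 5 days is not a failure, but not whether it triggers this censoring. The switch from darunavir to bictegravir that protocol 6.1.3 allows is not within class, so under the sentence its later viral loads would probably be dropped.
- The SAP does not say whether a stopped patient leaves the composite risk set or stays in it for clinical events only.

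No planned composite analysis clearly applies DPS1 to virological events. The PP/DPS2 analysis also drops post-stop virology. The snapshot and SAP 10.1.4 would show such stops but give no composite hazard ratio.

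**Working it through.** **1. Which rule applies to which part of the composite**

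| Source | Clinical events after a stop | Viral loads after a stop |
|---|---|---|
| DPS1 (SAP 5.2.1; 7.1 descriptive text) | kept | kept |
| SAP 7.1 censoring sentence; 7.2.1 | not mentioned, so kept | dropped |
| SAP 7.1 follow-up paragraph | kept | no end at treatment stop |
| DPS2 (PP sensitivity analysis) | dropped | dropped |
| Protocol 9.3 | kept while in the study | no rule for dropping them |

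Row two matches no defined data set. SAP 5.3 also sits badly with it: missing week-48 values of continuous endpoint variables may be replaced from the later visit even when the patient is off study drug.

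**2. The plan's own figures (SAP 4) reproduce**

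- Margin: ln(0.63)/ln(0.75) = 1.606. Expected hazard ratio: ln(0.77)/ln(0.75) = 0.909.
- Events: 4 × (1.960 + 0.842)² / [ln(0.909/1.606)]² = 96.9, so 97.
- Subjects: 97 / 0.24 = 404. Power with 97 events: 80.0%.

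**3. Illustration of size**

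The documents do not give the inputs needed, so these are assumptions:

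- *s* is the share of failures that could be lost: virological, shown only at week 48, with no clinical event. The planning figures suggest a ceiling of (25 − 12.2)/25 = 51%. It is not firm, because the 12.2% comes from another trial whose event list differs from this composite. I use 30% and 51%.
- *q* is the share of those whose drug is stopped first.
- Cox simulation, 202 per arm, non-inferiority if the upper 95% limit is below 1.606. Paired results are for stopped patients leaving the risk set / staying in it event-free.

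With no stopping, false non-inferiority at the margin (37% v 25%) is 2.8% and power (23% v 25%) is 79.7%.

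| Stopping, INI v PI | s = 30% | s = 51% |
|---|---|---|
| Equal, q from 10% to 25% | power 76.7–78.8% | power 74.3–77.9% |
| 10% v 25% (more PI) | power 71.4% / 70.2% | power 64.2% / 61.4% |
| 25% v 10% (more INI) | false NI 4.1% / 5.0% | false NI 5.5% / 7.2% |

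Equal stopping leaves false non-inferiority at 2.5–3.0%. With more PI stopping at s = 51% (staying) it falls to 0.9%. With more INI stopping, about 7 events (s = 30%) or 12 (s = 51%) are lost.

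**4. Hand check of one cell** (25% v 10%, s = 51%, staying)

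- INI risk: 0.37 × (1 − 0.51 × 0.25) = 0.3228. PI risk: 0.25 × (1 − 0.51 × 0.10) = 0.2372.
- Hazard ratio: ln(0.6772)/ln(0.7628) = 1.44. Events: 202 × (0.3228 + 0.2372) = 113. Standard error: √(4/113) = 0.188.
- False non-inferiority: Φ[(ln 1.606 − ln 1.44)/0.188 − 1.96] = 8.4%, against 7.2% simulated (hazard ratio 1.46).

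**5. Does using all observed data cure it?** In that same scenario the error is 2.4%, 4.3% or 7.2% if none, half or all of the stopped patients re-suppress by week 48. Counting the stop as failure gives 2.3%.

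**The case against.** The best defence is that the rule is deliberate. On-treatment virology also appears in SAP 7.2.1 and in the snapshots of 7.2.2 and 10.2.2, each of which names mITT and DPS1 nearby or falls under the 5.2.1 assignment. A specific sentence would normally prevail over a general label, and v0.3 is a draft with an update due before sign-off. It stands that the rule may be intended. But a snapshot classifies stopped patients, and counts efficacy stops against the regimen, whereas 7.1 censors them. Intention would also leave the two definitions missing.

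Exposure is narrow. A lost event needs a stop before any criterion is met, in a patient who remains in the study, and not through an adverse-event or IRIS interruption over 5 days, which is itself an endpoint. Protocol 6.7 has study drug stopped after virological failure, so many efficacy stops will follow the event. All of this stands and limits the size.

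Four stronger readings are tempting, and the documents do not support them:

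- *The primary analysis is really DPS2.* The sentence covers virological events only and does not mention rescue; DPS2 drops everything after a stop or rescue.
- *The protocol forbids the rule.* Section 9.3 is silent on viral loads after a drug stop. The rule is an unexplained addition to its censoring text, not a breach of an explicit ban.
- *The trial's false non-inferiority rate is inflated.* That needs more INI stopping, which nothing suggests. The only hints point the other way: the darunavir-to-bictegravir switch in protocol 6.1.3, and the fewer drug interactions expected on B/F/TAF in 1.2.2.
- *Deleting the sentence is enough.* Step 5 shows it is not if stopped patients re-suppress on rescue.

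**Conclusion.** The inconsistency is established from the text alone: the primary composite is assigned to one data set and its virological events are censored by a rule outside that data set, outside the follow-up paragraph and outside protocol 9.3. The resulting hybrid is undefined in two respects that affect the hazard ratio.

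Its numerical effect is hypothetical, because no stopping rates are given. Under the assumptions above, equal stopping mainly costs power (74–79% against about 80%). More PI stopping is conservative and costs more (61–71%). Only more INI stopping raises false non-inferiority, to 4–7% at 25% v 10%. The rating rests on the unresolved primary rule and the potential for informative censoring, not on these figures. Severity: SHOULD-FIX, before the SAP is signed.

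**What to change.** State one rule for virological events in the primary analysis and make SAP 5.2.1, both parts of 7.1, and 7.2.1 agree with it and with protocol 9.3.

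- **Reading that fits the SAP's DPS1 assignment and the protocol:** remove the censoring from 7.1 and 7.2.1, assess virological criteria on all viral loads to week 48, and keep on-treatment censoring as a labelled sensitivity analysis.
- **If on-treatment virology is intended:** change the DPS1 statements, define the hybrid, justify the departure from the protocol, and report the DPS1 composite hazard ratio beside it.

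Under either choice:

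- define treatment discontinuation for this analysis consistently with the within-class switch note;
- say whether a stopped patient stays in the risk set;
- add one composite sensitivity analysis that dates discontinuation for lack or loss of efficacy as virological failure at the stop, as the 7.2.2 snapshot does in classifying it;
- report by arm the number of stops and how many week-48 values were taken after one.

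The cost is SAP wording and the added sensitivity analysis, with no new data collection. The drawback of using all observed data is that post-stop viral loads will be incomplete and will partly reflect rescue therapy, so it does not by itself remove the bias. That is why the stop-as-failure analysis is needed.

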The efficacy and safety of B/F/TAF in virologically-suppressed HIV-1 infected adults are based on 48-week data from a randomised, double-blind, active-controlled study, GS-US-380-1844 ("Study 1844") (N=563); and a randomised, open-label, active-controlled study, GS-US-380-1878 ("Study 1878") (N=577).

The efficacy and safety of FTC+TAF (components of B/F/TAF) in HIV-1 infected, virologically-suppressed patients with mild to moderate renal impairment is based on 144-week data from an open-label study, GS-US-292-0112 ("Study 112") (N=242).

The efficacy and safety of FTC+TAF in adult patients coinfected with HIV-1 and chronic hepatitis B (HBV) are based on 48-week data from an open-label study, GS-US-292-1249 ("Study 1249") (N=72). The efficacy and safety of B/F/TAF in adult patients coinfected with HIV-1 and chronic HBV are also supported by 48-week data in 8 HIV/HBV coinfected adults treated with B/F/TAF in Study 1490 and 8 HIV/HBV coinfected adults treated with B/F/TAF in Study 1878.

Treatment-Naïve Patients

In Study 1489, patients were randomised in a 1:1 ratio to receive either B/F/TAF (N=314) or ABC/DTG/3TC (600/50/300 mg) (n=315) once daily. In Study 1490, patients were randomised in a 1:1 ratio to receive either B/F/TAF (N=320) or DTG+FTC/TAF (50+200/25 mg) (N=325) once daily.

In Studies 1489 and 1490, the mean age was 35 years (range 18-77), 89% were male, 58% were White, 33% were Black, and 3% were Asian. 24% of patients identified as Hispanic/Latino. The mean baseline plasma HIV-1 RNA was 4.4 log₁₀ copies/mL (range 1.3-6.6). The mean baseline CD4+ cell count was 460 cells/mm³ (range 0-1636) and 11% had CD4+ cell counts less than 200 cells/mm³. 18% of patients had baseline viral loads greater than 100,000 copies/mL. In both studies, patients were stratified by baseline HIV-1 RNA (<100,000 copies/mL, >100,000 copies/mL to ≤400,000 copies/mL, or >400,000 copies/mL), by CD4 count (<50 cells/µL, 50-199 cells/µL, or ≥200 cells/µL), and by region (US or ex-US).

Treatment outcomes of Studies 1489 and 1490 through Week 48 are presented in Table 1-1.

Table 1-1 Pooled Virologic Outcomes of Studies 1489 and 1490 at Week 48 in Treatment-Naïve Patients^a

	B/F/TAF (N=634) ^b		ABC/DTG/3TC (N=315) ^c	DTG+FTC/TAF (N=325) ^d
HIV-1 RNA < 50 copies/mL	91%		93%	
Treatment Difference (95% CI) B/F/TAF vs Comparator	-	-2.1% (-5.9% to 1.6%)	-1.9% (-5.6% to 1.8%)	
HIV-1 RNA ≥ 50 copies/mL ^e	3%	3%		1%
No Virologic Data at Week 48 Window	6%	4%		6%

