4. SAMPLE SIZE CALCULATION

In the ANRS 146 OPTIMAL trial [Levy et al.], of late presenters, the proportion of patients with severe morbidity (new adverse drug event (ADE), other HIV related diseases, serious non-AIDS events, IRIS and death) was estimated at 12.2% per year in the boosted PI arm. The virological failure was estimated at 20% at week 48 in the DRV/r group of the IMEA 040 DATA study (Slama L et al) that recruited a similar population. As a few subjects will meet more than one of these criteria, we assumed a cumulative probability of failure at 25% at 48 weeks in the PI regimen group.

A total of 404 evaluable subjects, randomized in a 1:1 ratio to 2 treatment groups (202 subjects per treatment group), achieves at least 80% power to detect a non-inferiority margin of 1.606 in the hazard ratio, which corresponds to a 12% difference in the cumulative probability of failure rate between INI-based regimen group (37%) and PI-based regimen group (25%), with 97 events required. The sample size and power calculation assume that the cumulative probability of failure is 25% for the PI regimen group and 23% for the INI-based regimen group (i.e. the expected hazard ratio is 0.909), using a non-inferiority margin of 1.606 in hazard ratio and a two-sided 95% confidence interval (CI). The sample size and power calculation were made using the statistical software package nQuery Advanced, non-inferiority testing of two survival curves using cox regression module (Version 8.1.2.0).

With an estimated ~7.5% drop off rate/year, we plan to enrol 220 subjects per group to ensure we have sufficient power for this per-protocol analysis.

Superiority of INI-based regimen group versus PI-based regimen group will be evaluated after the non-inferiority is established. With an ITT analysis, 440 subjects and 78 events, a two-sided log-rank test at an alpha level of 0.05 will achieve at least 80% power to detect a 50% reduction in hazard rate in INI-based regimen (i.e. the hazard ratio is 0.5). A 50% reduction in hazard rate means that INI-based regimen could decrease the risk by 11.6% (25% for PI- vs 13.4% for INI- based regimen).

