The effect of study treatment on the proportion of patients with HIV-RNA viral load <50 copies/ml at week 24, 36 and 48 will be assessed using a logistic regression model with treatment group and adjustments for stratification factor (country/group of neighbouring countries and baseline CD4 cell counts (<50 or \geq 50/ μ L)). An adjusted odds ratio (OR) and the associated 95% Confidence Interval (CI) will be calculated.

In addition, we will use Cochran-Mantel-Haenszel tests to assess the difference between treatments in the percentage of participants with HIV-RNA viral load <50 copies/ml at week 48 (ie, response rate in BIC group minus the response rate DRV/c group) adjusted for country/group of neighbouring countries and baseline CD4 cell counts (<50 or \geq 50/ μ L). All P-values will be two-tailed with a significant level at 5%.

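### Baseline viral load is missing from the primary and suppression models, and the randomisation factors are coarsened on a weak sample-size ground; the loss is modest and spares non-inferiority power

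*Combined protocol and SAP*

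**What the plan says.** SAP 7.1: "The effect of study treatment will be assessed using Cox regression model with treatment group and adjustments for stratification factor". The factors are country (or a group of neighbouring countries) and CD4 below 50 versus 50 and above. The reason given is "as the sample size would not allow use of the stratification factors of randomisation".

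SAP 6.5 adds detail. Seven countries by three CD4 levels make 21 strata, some expected to be thin. Countries recruiting fewer than 10 are to be joined with neighbours, without saying which. The two upper CD4 levels are merged because few participants are expected at 200 or more.

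SAP 7.2.2, on suppression at weeks 24, 36 and 48, says the treatment effect "will be assessed using a logistic regression model with treatment group and adjustments for stratification factor", with the same coarsened factors. SAP 10.2.2 repeats this for weeks 4, 8 and 12.

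Protocol 9.3.2, in both v1.5 and v5.0, adjusts the primary Cox model for participating country and baseline CD4 and mentions no grouping. Randomisation (protocol 6.1.5, SAP 3.2) is stratified on country and three CD4 levels, not on viral load.

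Baseline viral load is summarised in SAP 6.3.2 ("HIV RNA viral load, log10 copies/mL and in category") and is a subgroup variable in SAP 9. Of the two phase 3 trials described in protocol 1.2.1, the protocol says: "In both studies, patients were stratified by baseline HIV-1 RNA". No reason is given for leaving it out of the models; the sample-size reason is attached only to the coarsening.

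**The concern.** The planning text puts virological failure at 20% at week 48 within an assumed 25% composite, and one component, the week-12 fall of less than 1 log10, is defined relative to baseline HIV RNA. Baseline viral load is therefore a natural covariate. Because allocation is not balanced on it by design, any chance imbalance stays in the hazard ratio and in the odds ratios for suppression.

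The coarsening is a separate matter. An argument from 21 thin strata applies to a stratified or interaction model. The SAP describes adjustment, which as main effects needs far fewer parameters. The result departs from both the randomisation and protocol 9.3.2, and in an open-label trial the unnamed country groups leave part of the primary model open until recruitment is known.

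**Working it through.** **1. The plan's own figures** (SAP 4). Margin: ln(0.63)/ln(0.75) = 1.606. Expected hazard ratio: ln(0.77)/ln(0.75) = 0.909. Events: 4(1.960 + 0.842)² / [ln(1.606/0.909)]² = 96.9, so 97. Subjects: 97/0.24 = 404. For superiority, 220 × 0.25 + 220 × 0.134 = 84.5, and 84.5 × 0.925 = 78 events; power at hazard ratio 0.5 is 86%, in line with the stated minimum of 80%. All reproduce.

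**2. Parameter count for main effects.**
- Arm 1 + country 6 + CD4 2 = 9, and 97/9 = 10.8 events per parameter.
- With linear log10 viral load: 97/10 = 9.7.
- With the 11 countries that the protocol v5.0 synopsis allows: 1 + 10 + 2 = 13, and 97/13 = 7.5.
- All 21 strata as one factor: 20 + 1 = 21, and 97/21 = 4.6.
- Superiority, 78 events: 78/9 = 8.7.
- Suppression, if 20% of 440 are unsuppressed: 88/9 = 9.8.

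**3. Chance imbalance.** The standard error of the between-arm difference in mean viral load is √(2/220) = 0.095 SD. For an assumed hazard ratio per SD of 1.3, 1.6 or 2.0, a one-standard-error imbalance moves the hazard ratio by about 2.5%, 4.6% or 6.8%. The standard error of the log hazard ratio at 97 events is 2/√97 = 0.20.

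**4. Simulated power (%)**, 440 subjects, 7.5% dropout, 1500 trials per Cox scenario and 2000 per logistic scenario. Columns give the assumed viral-load effect (hazard or odds ratio per log10).

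| Test | Model | 1.0 | 1.5 | 2 | 3 |
|---|---|---|---|---|---|
| Non-inferiority, 25% v 23% | SAP | 81.8 | 81.3 | 81.5 | 82.7 |
| | full factors | 81.3 | 80.9 | 81.2 | 82.3 |
| | full + viral load | 81.2 | 81.7 | 82.0 | 81.8 |
| Superiority, 25% v 13.4% | SAP | 85.7 | 86.2 | 84.8 | 87.4 |
| | full factors | 85.8 | 86.2 | 84.7 | 87.3 |
| | full + viral load | 85.6 | 86.7 | 86.1 | 91.4 |
| Week-48 logistic, 20% v 10.5% | SAP | 80.6 | 79.7 | 78.9 | 80.1 |
| | full factors | 80.3 | 79.8 | 78.8 | 79.7 |
| | full + viral load | 80.1 | 79.5 | 80.6 | 83.0 |

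Restoring the factors changes power by -0.5 to +0.1 points. Against the SAP model, adding viral load as well changes non-inferiority by -0.9 to +0.5, superiority by -0.1 to +4.0 and the logistic model by -0.5 to +2.9.

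Other assumptions, not in the documents, give larger gains over an unadjusted model. At 25% v 16% with a hazard ratio per SD of 1.3, 1.6 or 2.0, superiority power goes from 64, 63, 64 to 66, 66, 70. At 70% v 80% suppressed with an odds ratio per SD of 2.0, 2.5 or 3.0, it goes from 69, 70, 68 to 71, 75, 77.

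**5. The margin.** If the true risks are 37% v 25%, the conditional hazard ratio with viral load in the model is 1.62, 1.65 or 1.71 for a viral-load hazard ratio of 1.5, 2 or 3, not 1.606. The chance of declaring non-inferiority there is 1.9%, 1.3% and 1.5%, against 2.2%, 2.3% and 2.9% with the full factors alone.

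**6. Sparse levels.** With one country at an assumed 2% of patients, a country coefficient diverged in 7 to 23% of simulated trials with ungrouped countries, against 0.5 to 5% under the SAP model. The treatment estimate was barely affected.

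Assumed, not in the documents: the prognostic strength of viral load, its SD (0.7 log10), the country and CD4 mix (50/42/8%) and effects, exponential event times, and 10.5% failure in the integrase arm for the logistic check.

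**The case against.** Adjusting for stratification factors is conventional, viral load was not one here, and chance imbalance does not invalidate a randomised test. The primary test is non-inferiority against a fixed hazard-ratio margin, where step 4 shows nothing to gain. No document states how prognostic viral load is. Protocol 1.2.1 reports outcomes in the two phase 3 trials as similar across subgroups including baseline viral load; this may describe treatment comparisons, but it does not support a strong gradient. All of this stands, and it limits the point.

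The sparsity argument stands in part. A country with a handful of patients can have an unstable coefficient even as a main effect, and SAP 6.5 groups only countries with fewer than 10. Cell sparsity also matters for the week-48 Cochran-Mantel-Haenszel analysis in SAP 7.2.2, which stratifies. The count of 9 rests on seven countries and would be 13 with eleven; the separate component analyses will have fewer events than 97. None of this makes the full factors unworkable in the primary Cox model as the SAP describes the trial.

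A reader might infer that the omission gives up primary power and could be repaired at no cost. Neither is supported: non-inferiority power is unchanged, and adding viral load loosens the link between 1.606 and the 12-point difference. A reader might also take 20% of 25% to mean that most failures will be virological. The 20% and the 12.2% severe-morbidity figure come from two different trials and overlap, and viral load above 50 counts only at week 48, after earlier clinical events. Virological-first failure could be as low as 25 - 12.2 = 12.8 points, about half.

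**Conclusion.** The point holds as a modest improvement. The sample-size reason does not bear out the coarsening when the factors enter as main effects: 10.8 events per parameter with the SAP's seven countries. The SAP also departs from protocol 9.3.2. Correcting this buys consistency with the randomisation and the protocol, and a closed specification, but no measurable power.

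Leaving out baseline viral load does not affect non-inferiority power. It forgoes roughly 0 to 4 points for superiority at the planned effect and for suppression, the upper end only if viral load is strongly prognostic (about 3 per log10), and it leaves a removable imbalance of about 0.1 SD in the estimates. The larger gains in step 4 need a smaller treatment effect than planned, or a steep viral-load gradient for suppression. The adjusted ratio is conditional and slightly further from 1, which is conservative at the margin. For that reason the non-inferiority model should not simply be replaced.

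**What to change.** Before database lock:

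1. Add continuous baseline log10 HIV RNA to the logistic models in SAP 7.2.2 and 10.2.2 and to the Cox model used for superiority.
2. For non-inferiority, keep the Cox model with stratification factors only as primary, so that 1.606 retains its 12-point meaning, and pre-specify the viral-load-adjusted Cox model as a sensitivity analysis.
3. Enter country and three-level CD4 as main effects, as randomised. Pool only countries with fewer than 10 participants, into groups named in advance. Replace the sample-size sentence and reconcile SAP 7.1 with protocol 9.3.2.

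The cost is mainly wording: the SAP is version 0.3, and its sections 1.1 and 5.1 provide for updating and signing before the final analysis. Protocol 9.8 sends major changes to the analysis through a protocol amendment, so the sponsor should decide whether item 1 counts as one; item 3 brings the SAP back towards the protocol. The remaining downsides are a conditional estimate that needs labelling as such, and a possibly unstable coefficient for a very small country or CD4 level, with little effect on the treatment estimate.
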